#### 6.5 STUDY CONDUCT DURING COVID-19

In March 2020, the World Health Organization declared a global pandemic related to an illness caused by a novel coronavirus known as COVID-19. Alternative procedures and allowances are permitted due to restrictions related to COVID-19, including delays to in-person visits and specific assessments, performing remote phone or video visits if in-person visits cannot be conducted, and arranging shipments of investigational product directly to subjects. These allowances are detailed in [Appendix 11](#). Though every attempt should be made to conduct study visits as described in this protocol, any implementation of alternative processes should be properly documented, including what was done differently, which assessments or visits were missed or performed via phone or video.

## 7. EFFECTIVENESS, SAFETY, AND PHARMACOKINETIC ASSESSMENTS

For an overview of the study variables and measurement times, see Schedule of Assessments (Table 1 and Table 2).

Variables used to measure treatment compliance with respect to administration of the IMP are described in Section 5.7.

### 7.1 EFFECTIVENESS ASSESSMENTS

For all questionnaires and rating scales, the same evaluator (at the clinical site and parent/caregiver) will complete the assessments for the duration of the study. Substitutions at the clinic with another rater that has established inter-rater reliability is acceptable on an infrequent basis. For the in-clinic questionnaires and rating scales completed by the parent/caregiver, if the same parent/caregiver cannot complete the questionnaire/rating scale at a visit, the questionnaire/rating scale will not be completed. For the diary, the same parent/caregiver will complete all entries throughout the study.

#### 7.1.1 Seizure Assessments

Seizure frequency by type and duration (< 2 minutes, 2-10 minutes, > 10 minutes) will be recorded daily by the parent/caregiver in a diary. Seizure types include:

- A: Hemiclonic (note lateralization – right body, left body, or independent right and left)
- B1: Focal With or Without Clear, Observable Motor Signs
- B2: Focal Without Clear, Observable Motor Signs
- C: Secondarily Generalized Tonic Clonic (evolving to bilateral convulsive seizure from focal seizure)
- D: Generalized Tonic Clonic Convulsion
- E: Absence or Atypical Absence
- F: Myoclonic
- G: Tonic
- H: Atonic
- I: Clonic
- J: Tonic/Atonic (cannot differentiate; also known as ‘drop attack’)
- K: Infantile Spasms (if under 3 years of age)
- L: Epileptic Spasms (if 3 years of age and older)
- O: Other

Effectiveness endpoints that will be derived from the diary data include frequency of convulsive seizures and of all seizures, and the number/duration of seizure free intervals.

Seizures that evolve into SE will be captured by type and duration (> 10 minutes) as are all seizures. The diagnosis of SE should be entered as an AE or SAE if a prolonged seizure or series of seizures persists for 30 minutes or longer, regardless of administration of rescue medication. If this incident involves multiple seizures close in time, the SE definition applies if the seizures are close together such that consciousness is not regained between ictal events.

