## 2.4 STUDY ENDPOINTS

### 2.4.1 Effectiveness Endpoints

The effectiveness endpoints of the study are:

- Number of seizures by type
- Convulsive seizure-free interval
- CGI-I as assessed by parent/caregiver
- CGI-I as assessed by principal investigator
- QOLCE to measure changes in quality of life of the subject
- PedsQL to measure changes in quality of life of the subject
- PedsQL Family Impact module to measure changes in quality of life of the parent/caregiver
- QoL of parent/caregiver using the EQ-5D-5L scale
- Affective symptoms of parent/caregiver using the HADS (in parents/caregivers from core studies ZX008-1501 and ZX008-1502 only)
- Duration of prolonged seizures (seizure type that, during pre-Z008 baseline, had duration > 2 minutes)
- Number of episodes of SE
- Number of instances of rescue medication use and number of doses
- Number of inpatient hospital admissions due to seizures

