  - a. Onset of seizures in the first year of life in an otherwise healthy infant.

- b. A history of seizures that are either generalized tonic-clonic or unilateral clonic or bilateral clonic, and are prolonged.
  - c. Initial development is normal.
  - d. History of normal brain MRI without cortical brain malformation.
  - e. Lack of alternative diagnosis.
  - f. Meets one of the following 3 confirmatory diagnostic criteria:
    - i. Emergence of another seizure type, including myoclonic, generalized tonic-clonic, tonic, atonic, absence and/or focal has developed after the first seizure type.
    - ii. Prolonged exposure to warm temperatures induces seizures and/or seizures are associated with fevers due to illness or vaccines, hot baths, high levels of activity and sudden temperature changes and/or seizures are induced by strong natural and/or fluorescent lighting, as well as certain visual patterns.
    - iii. Genetic test results consistent with a diagnosis of Dravet syndrome (pathogenic, likely pathogenic, variant of unknown significance, or inconclusive but unlikely to support an alternative diagnosis.)
  - g. Subject has been approved for study inclusion by the Epilepsy Study Consortium.
  - h. Subject does not have an exclusionary cardiovascular or cardiopulmonary abnormality based on ECHO, ECG or physical examination and is approved for entry by the central cardiac reader. Exclusionary abnormalities include, but are not limited to:
    - i. Mild or greater mitral or aortic valve regurgitation in subjects >18 yrs of age
    - ii. Possible signs of pulmonary hypertension with abnormal or greater than upper limit of normal values
    - iii. Evidence of diastolic dysfunction
  - i. Subject must have had  $\geq 4$  convulsive seizures (tonic, tonic-atonic, tonic-clonic, clonic) per 4-week period for past 12 weeks prior to screening, by parent/guardian report to investigator or investigator medical notes.
  - j. All medications or interventions for epilepsy (including ketogenic diet [KD] and vagal nerve stimulation [VNS]) must be stable for at least 4 weeks prior to screening and are expected to remain stable throughout the study.
11. Subject's parent/caregiver is willing and able to be compliant with diary completion, visit schedule and study drug accountability.

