### 10.5.2 Effectiveness Analyses

#### 10.5.2.1 Key Effectiveness Analysis

The key effectiveness endpoint is the change in the convulsive seizure frequency per 28 days between the pre-ZX008 Baseline and OLE Treatment Period. The frequency of convulsive seizures during a given period will be derived from the number and type of events recorded in subject diaries. The seizure frequency per 28 days will be calculated as the number of seizures recorded divided by the number of days in the period and multiplied by 28. The convulsive

seizure frequency will be calculated from all available data collected during either the pre-ZX008 Baseline or OLE Treatment Periods.

Both the mean and median frequency of convulsive seizures will be presented for the pre-ZX008 Baseline Period and the OLE Treatment Period. The significance of the change between periods will be assessed using an analysis of covariance (ANCOVA) model with age group (< 6 years, ≥ 6 years) as a factor and with pre-ZX008 baseline frequency as a covariate. Other factors may be included in the model if they are found to be informative during analyses of the core studies.

Since the ANCOVA relies on assumptions of normality, the key effectiveness endpoint will also be analyzed using a nonparametric method that does not require as stringent assumptions. A test such as the stratified Wilcoxon signed rank test will be used to assess the change from baseline while stratifying by age group.

An additional analysis will be performed to assess the sensitivity of the key effectiveness analysis to changes in dose or type of concomitant AED medications that may occur during the course of the trial. Specifically, the analysis will be repeated with a factor added to the model to indicate whether a subject had a change in prescribed dose or type of concomitant AED medication during the OLE Treatment Period. Further exploratory analyses may be conducted if changes in concomitant AED medication appear to have a significant impact on the effectiveness of ZX008.

Only subjects from Studies ZX008-1501, ZX008-1502, and Cohort 2 of ZX008-1504 will be included in change from baseline analyses of effectiveness. Subjects from Study ZX008-1504 Cohort 1 will be excluded from such analyses since they will enter the OLE Treatment Period without first participating in a baseline period that includes a formal assessment of pre-ZX008 seizure frequency.

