#### **10.5.2.2 Other Secondary Analyses**

Methods similar to those used for the key effectiveness analysis will also be used to assess the change in frequency of non-convulsive seizures and the composite endpoint of non-convulsive plus convulsive seizures. The proportion of subjects who achieve a ≥40% reduction from baseline in convulsive seizure frequency, along with its 95% CI, will be reported. A similar summary will be reported for the proportion of subjects who achieve a ≥50% reduction from baseline. The analyses will be performed using data collected over the open label OLE Treatment Period.

The longest interval between convulsive seizures will be calculated for each subject over the entire OLE Treatment Period. The median interval will be presented.

Palatability will be assessed through descriptive statistical methods. For example, the percentage of parents or caregivers who consider the medicine's taste and texture to be acceptable to the subject will be presented along with a 95% CI at each time point data are available.

QoL measures will be summarized by descriptive statistic for each time point where they are obtained. Where appropriate, the significance of the change from baseline will be assessed using mixed effects models for repeated measures.

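### Diary code B1 contains all of code B2, so the split of focal seizures between the two codes is not determined

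*Protocol*

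**What the plan says.** Protocol section 7.1.1 has seizure frequency by type and duration, which "will be recorded daily by the parent/caregiver in a diary". It lists 14 type codes: A, B1, B2, C to L, and O. The two at issue are "B1: Focal With or Without Clear, Observable Motor Signs" and "B2: Focal Without Clear, Observable Motor Signs". Focal seizures that evolve into bilateral convulsive seizures have their own code, C.

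The codes are used as follows:
- Section 2.4.1 lists "Number of seizures by type" as an effectiveness endpoint. It also lists the duration of prolonged seizures, where the seizures to follow are picked out by type: those types that lasted over 2 minutes in the pre-ZX008 baseline.
- Section 10.5.2.1, on the key effectiveness endpoint: "The frequency of convulsive seizures during a given period will be derived from the number and type of events recorded in subject diaries".
- Section 10.5.2.2 applies similar methods to the "change in frequency of non-convulsive seizures and the composite endpoint of non-convulsive plus convulsive seizures".

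The only list of convulsive types in the protocol is the entry criterion for de novo subjects (section 4.1, criterion 10i, repeated in the synopsis and in a footnote to Table 1): "convulsive seizures (tonic, tonic-atonic, tonic-clonic, clonic"). No focal type is named there.

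**The concern.** Two separate focal codes serve a purpose only if they divide focal seizures by the presence of motor signs. As written they do not, because B1 takes both kinds. A caregiver who follows the text can enter a focal seizure without motor signs under either code, and two caregivers can both be right while recording the same event differently.

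The fault lies where the data are recorded, so it cannot simply be left to the statistical analysis plan. Once a seizure without motor signs has been entered as B1, no later rule can separate it from the motor focal seizures under that code. What is at stake is the meaning of the B1 and B2 lines in a listed endpoint, and of any comparison of those lines between baseline and the open-label period.

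**Working it through.** The protocol states no figure on this point, so the check is a logical one.

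**Step 1: the sets.** Let *m* be a subject's focal seizures with motor signs in a period and *n* those without, leaving aside seizures that belong under another code. As written, B1 accepts both *m* and *n*, and B2 accepts *n* only. B2 is a subset of B1, and the overlap is all of B2.

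**Step 2: what the overlap leaves open.** Assume each seizure is entered once, under one code. Let *k* of the *n* seizures be entered as B1, with *k* anywhere from 0 to *n*. Then:
- B1 count = *m* + *k*, anywhere from *m* to *m* + *n*.
- B2 count = *n* − *k*, anywhere from *n* down to 0.
- B1 + B2 = (*m* + *k*) + (*n* − *k*) = *m* + *n*, whatever *k* is.

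The split is free over the whole of *n*, while the sum is fixed. For example, with *n* = 6 per 28 days (an assumed number, since the protocol gives no shares by type), the B2 count could be anything from 0 to 6 with no change in the subject. The remaining 14 − 2 = 12 codes and the all-seizure total do not contain *k*.

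**Step 3: is there a rule that fixes *k*?** Section 7.1 keeps the same parent or caregiver on the diary throughout. Sections 6.1.3 and 6.1.4 have the site review the diary at visits, and section 9.1 has the investigator review entries for completeness and consistency. None of these says which code applies. No other section defines B1 or B2, and the listed changes of Amendment 5.0 do not touch the code list.

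**Step 4: other uses of type.** For the prolonged-seizure endpoint, if the diary code is what counts as a type, a long focal seizure without motor signs at baseline makes B1 or B2 a qualifying type depending on how it was entered. That in turn decides which later seizures are followed.

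**Step 5: convulsive and non-convulsive frequencies.** If B1 and B2 fall on the same side of the split, both frequencies and their composite depend only on *m* + *n*, so *k* drops out. If B1 is convulsive and B2 is not, the convulsive count contains *m* + *k* and the non-convulsive count contains *n* − *k*. Only in that second case does the overlap reach these endpoints, and the composite is still unaffected.

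**The case against.** The strongest reply is that this is a plain wording slip: the presence of B2 shows that B1 was meant for focal seizures with motor signs, and most readers would take it so. One caregiver per diary and regular site review make a systematic switch between periods less likely. Section 10.5.2 plans no test on B1 or B2 separately, and the primary objective is safety. The diary itself is not shown and may carry the right wording.

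Much of this stands, and it limits the point to a small correction. It does not remove it. The intended meaning is an inference, and the consistency measures do not tell a caregiver which code to use.

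A reader might go further and infer that the key endpoint is at risk. Suppose 10 convulsive and 6 non-motor focal seizures per 28 days, no drug effect, B1 counted as convulsive and B2 not, and all six entered as B1 at baseline and B2 afterwards. The convulsive count then falls from 16 to 10, (10 − 16)/16 = −37.5%. The reverse switch gives (16 − 10)/10 = +60%. With 1 to 3 such seizures the spurious fall is 1/11 = 9.1% to 3/13 = 23.1%.

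The documents do not support that reading. The protocol never classes B1 as convulsive. Its one list of convulsive types names no focal type, although an entry criterion for de novo subjects need not be exhaustive. Section 1.1 describes focal seizures as a group apart from convulsive ones. Complete recoding between periods is a further assumption, and even then −37.5% falls short of the lowest responder cut of 40%.

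**Conclusion.** The code list is wrong as written. B1 contains B2, so the division of focal seizures between these two codes is undetermined within a listed endpoint and within any classification by type that relies on the codes. The size is bounded: 2 of 14 codes, and within them the number of focal seizures without motor signs, which the protocol does not give. The sum of the two codes, the other 12 codes and the all-seizure total stand, provided each seizure is entered once.

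An effect on convulsive or non-convulsive frequency is conditional on the two codes lying on different sides of that split. The protocol does not say so, and the statistical analysis plan was not available to this review. The lack of a code-to-convulsive mapping in the protocol is not itself a fault, since such derivation detail is commonly left to that plan. Whether collected data are affected depends on the label printed in the diaries, which only the sponsor can check.

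**What to change.** 1. In section 7.1.1, delete the two words *or Without* from B1, so that B1 and B2 are mutually exclusive.
2. Check the wording against the diary in use and against the core-study diaries. For subjects from ZX008-1501, ZX008-1502 and ZX008-1504 Cohort 2, section 10.4 takes the pre-ZX008 baseline from the core study, so both ends of the comparison matter.
3. If the diaries already separate the two kinds, nothing more is needed.
4. If they carry the overlapping label, do not split B1 from B2 for data already collected: report them combined. Section 1.3 puts enrolment at 330 by the October 2019 cut-off, so much of the data predates any relabelling. A split introduced part-way would have no counterpart at baseline, so comparisons with baseline should stay on the combined count.
5. Only if the two codes fall on different sides of the convulsive/non-convulsive split, and the overlap was in the diary, add one sensitivity analysis with B1 moved to the other side.

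The cost is one line of protocol text, a check of the diary wording, possibly a diary label change, and at most one extra analysis.

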### 7.1.2 Clinical Global Impression - Improvement

Both the parent/caregiver and the investigator will rate their global impression of the subject's condition throughout the study according to the schedule in **Table 1** and **Table 2**.

The Clinical Global Impression (CGI) scale measures the change in the subject's clinical status from a specific point in time. The CGI rating scale permits a global evaluation of the subject's improvement over time. The severity of a patient's condition is rated on a 7-point scale ranging from 1 (very much improved) to 7 (very much worse) as follows:

- 1=very much improved
- 2=much improved
- 3=minimally improved
- 4= no change
- 5=minimally worse
- 6=much worse
- 7=very much worse

The parent/caregiver will be asked to indicate the appropriate response that adequately describes how their child's symptoms have improved or worsened relative to baseline before the beginning of the core study (before any study drug was taken).

The investigator will be asked to indicate the appropriate response that adequately describes how the subject's symptoms have improved or worsened relative to baseline before the beginning of the core study (before any study drug was taken).

### 7.1.3 Quality of Life in Childhood Epilepsy Scale

The QOLCE ([Appendix 4](#)), a low-burden parent/caregiver completed assessment that looks at how epilepsy affects day-to-day functioning of their child in various life areas, including physical activities, well-being, cognition, social activities, behavior and general health, will be conducted according to the schedule in [Table 1](#) and [Table 2](#). The QOLCE has been validated in children aged 4 and older, and there are published data on the use of the QOLCE in children with epilepsy as young as 2 years of age ([Sabaz 2000](#); [Talarska 2007](#)).

#### 7.1.4 Pediatric Quality of Life Inventory (PedsQL)

The PedsQL ([Appendix 6](#)) is a pediatric modular measure of health-related QoL completed by the parent/caregiver on behalf of the subject. It consists of 4 core scales that measure physical, emotional, social, and school functioning. The PedsQL will be conducted according to the schedule in [Table 1](#) and [Table 2](#). The PedsQL will only be conducted in subjects who enter from the core studies (ie, PedsQL will not be performed on de novo subjects >18 years of age).

#### 7.1.5 Parent/Caregiver Quality of Life

The impact on the quality of life of the parent/caregiver responsible for a patient with DS will be assessed according to the schedule in [Table 1](#) and [Table 2](#) using 3 scales: the EQ-5D-5L, the HADS, and the PedsQL Family Impact Module. Parents/caregivers who do not give consent to collect these ratings scales will not complete them. The same parent/caregiver should complete these ratings throughout the study. If that person is not available at the visit, the scales should not be completed.

The EQ-5D-5L ([Appendix 7](#)) is a standardized measure of health status used to provide a simple, generic assessment for clinical and economic appraisal. It consists of 6 questions and can be completed in less than 10 minutes.

The HADS ([Appendix 8](#)) is a tool commonly used to determine the levels of anxiety and depression that a person is experiencing. It is a 14-item scale that generates ordinal data. Seven of the items relate to anxiety and 7 relate to depression.

The PedsQL Family Impact module ([Appendix 6](#)) is designed to measure the impact of pediatric chronic health conditions on parents and the family by measuring parent self-reported physical, emotional, social, and cognitive functioning, communication, worry, and family daily activities relationships. The PedsQL Family Impact module will not be assessed in the Netherlands.

The parent/caregiver will be asked to indicate the appropriate response that adequately describes how the care of their child with DS has impacted their quality of life using the scales described above.

#### 7.1.6 Study Medication Palatability Assessment

The palatability and overall acceptability of the IMP will be assessed indirectly by the parent/caregiver responsible for the patient according to the schedule in [Table 1](#) and [Table 2](#) using 3 questions:

QUESTION 1: Over the past month, on the basis of the reaction/ facial expression of your child, do you think that the medicine's taste and texture are:

- Acceptable to your child
- Not acceptable to your child

QUESTION 2: Over the past month, please rate how much your child likes/dislikes the medicine's taste using the following grading scale:

- 5 (likes it very much)
- 4 (likes it)
- 3 (neither likes it or dislikes)
- 2 (dislikes it)
- 1 (dislikes it very much)

QUESTION 3: Over the past month, do you sometimes have problems giving the medicine to your child due to its taste or texture?

- No
- Yes
  - How often?
    - Every day in the past month
    - Once to several times every week in the past month
    - Once or several times in the past month

## 7.2 EXPLORATORY ASSESSMENTS

The following exploratory assessments will be conducted for subjects who participated in core study ZX008-1504 only.

### 7.2.1 Sleep Quality and Meal Time Behavior Questions

The parent/caregiver will be asked to indicate the appropriate response that adequately describes their child's sleep quality and eating behavior since starting IMP based on the following questions:

*I. Since your child has started taking the study medication in this study, have you noticed that s/he has been waking in the middle of the night or very early in the morning more than usual?*

- My child's sleep is more disturbed than it was before s/he started the study medication
- My child's sleep patterns are the same as they were before starting the study medication
- My child sleeps better than s/he did before starting the study medication

2. Since your child has started taking the study medication in this study, have you noticed that s/he has had a change in their mealtime behavior?

- My child has worse meal time behavior since starting the study medication
- My child's meal time behavior has not changed since starting the study medication
- My child has improved his/her meal time behavior since starting the study medication

